### **3.1.4 Dose Limiting Toxicity**

The incidence of DLT(s) assessed in the first 3-6 evaluable subjects per tumor type (if applicable) during the first 6 weeks will be used to initially determine whether a dose level is tolerable. A subject will be considered evaluable for DLT if they have received at least 5 out of 6 ulocuplumab doses and at least 2 out of 3 nivolumab doses in a 6 week dosing period or experienced a DLT. DLT should not be AE considered by the investigator to be disease related. The following drug-related AE (whether related to one or both agents) will be considered a DLT:

- Any Grade  $\geq 3$  drug-related non-hematological AE, including the following laboratory abnormalities
  - If a subject has baseline Grade  $\leq 1$  AST, ALT, or total bilirubin, a drug-related Grade  $\geq 3$  toxicity will be considered a DLT
  - If a subject has baseline Grade 2 AST or ALT, drug-related elevations in AST and/or ALT  $> 2x$  baseline or a maximum of  $> 8x$  ULN will be considered a DLT
- Any Grade 4 drug-related hematological AE or hematological or non-hematological laboratory abnormality with the following exceptions:
  - Grade 4 amylase or lipase not associated with symptoms or clinical manifestations
  - Grade 4 lymphocytopenia not associated with symptoms or clinical manifestations
- Any drug-related AE that results in dose reduction of ulocuplumab during the DLT period
- Any drug related AE that results in dose delay of ulocuplumab  $> 14$  days during DLT period
- Any toxicity managed by discontinuation of ulocuplumab (see [section 4.5.3.1](#))
- Any toxicity managed by discontinuation of nivolumab (see [section 4.5.3.2](#))

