##### **4.5.1 Dose Delays and Interruptions**

###### **4.5.1.1 Ulocuplumab Dose Delay**

Investigators should, whenever possible, determine which medication is causing the toxicity and delay or dose reduce ulocuplumab and/or delay nivolumab, as applicable. If ulocuplumab is delayed due to an AE, nivolumab dosing may continue at the discretion of the Investigator. Ulocuplumab should be delayed for the following:

- Any Grade  $\geq 3$  drug-related AE, including laboratory abnormalities except for Grade 3 AEs that do not require nivolumab dose delay (see [section 4.5.1.2](#))

If the decision is to resume ulocuplumab dosing, the subject should restart treatment on the next regularly scheduled ulocuplumab dosing visit. Skipped doses are not to be replaced. If treatment is delayed > 6 weeks, the subject must be permanently discontinued from ulocuplumab therapy.

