#### **4.5.1.2 Nivolumab Dose Delay**

Investigators should, whenever possible, determine which medication is causing the toxicity and delay or dose reduce ulocuplumab and/or delay nivolumab, as applicable. If nivolumab is delayed due to an AE, ulocuplumab dosing should also be delayed. Nivolumab should be delayed for the following:

- Any Grade  $\geq 2$  non-skin, drug-related AE, with the following exceptions:
  - Grade 2 drug-related fatigue or laboratory abnormalities do not require a treatment delay
- Any Grade 3 skin drug-related AE
- Any Grade  $\geq 3$  drug-related laboratory abnormality, with the following exceptions for thrombocytopenia, lymphocytopenia, AST, ALT, total bilirubin or asymptomatic amylase or lipase:
  - Grade 3 thrombocytopenia  $< 7$  days (not associated with Grade  $\geq 2$  hemorrhage) does not require dose delay
  - Grade 3 lymphocytopenia not associated with symptoms or clinical manifestations does not require dose delay. It is recommended to consult with the BMS Medical Monitor for Grade 3 lymphocytopenia.
  - Grade 3 drug-related amylase or lipase abnormality that is not associated with symptoms or clinical manifestations of pancreatitis does not require dose delay. It is recommended to consult with the BMS Medical Monitor for Grade 3 amylase or lipase abnormalities
  - If a subject has baseline AST, ALT, or total bilirubin that is within normal limits, delay dosing for drug-related Grade  $\geq 2$  toxicity
  - If a subject has baseline AST, ALT, or total bilirubin within the Grade 1 toxicity range, delay dosing for drug-related Grade  $\geq 3$  toxicity
  - If a subject has baseline AST or ALT within the Grade 2 toxicity range, delay dosing for drug-related elevations in AST and/or ALT  $> 2x$  baseline or a maximum of  $> 8x$  ULN
- Any adverse event, laboratory abnormality, or intercurrent illness which, in the judgment of the investigator, warrants delaying the dose of study medication

If the decision is to resume nivolumab dosing, the subject should restart treatment on the next regularly scheduled nivolumab dosing visit. Skipped doses are not to be replaced. If treatment is delayed  $> 6$  weeks, the subject must be permanently discontinued from all study therapy, except as specified in [Section 4.5.3.2](#).

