**Table 4.5.2.1-1: Ulocuplumab Dose Modification Criteria**

Adverse Event	Dose Delay (refer to section 4.5.1.1)	Criteria to Resume Ulocuplumab Treatment			
		For DL-1	For DL1	For DL2	For DL3A/3B
Any Gr ≥ 3 drug-related AE, including laboratory abnormalities, except for Grade 3 hematologic AEs listed below or other exceptions listed in section 4.5.1	Hold ulocuplumab until return to baseline or Grade ≤ 1, whichever is lower	1st event: Discontinue ulocuplumab	1st event: Resume at 200 mg weekly	1st event: Resume at 400 mg weekly	1st event: Resume at 800 mg weekly
			2nd event: Discontinue ulocuplumab	2nd event: Resume at 200 mg weekly	2nd event: Resume at 400 mg weekly
				3rd event: Discontinue ulocuplumab	3rd event: Discontinue ulocuplumab
Any Gr3 drug-related neutropenia, Gr3 thrombocytopenia > 7 days	Hold ulocuplumab until return to baseline or Grade ≤ 1, whichever is lower	2nd event: Discontinue ulocuplumab	1st event: Resume at 200 mg weekly	1st event: Resume at 400 mg weekly	1st event: Resume at 800 mg weekly
			3rd event: Discontinue ulocuplumab	2nd event: Resume at 200 mg weekly	2nd event: Resume at 400 mg weekly
				3rd event: Discontinue ulocuplumab	3rd event: Discontinue ulocuplumab
Gr4 asymptomatic lipase or amylase elevations	Hold ulocuplumab until return to baseline or Grade ≤ 1, whichever is lower	All events: Resume at same dose. Consult with BMS Medical Monitor if recurrent or sustained.			

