**Table 5.1-2: On-Study Assessments for Dose Evaluation Phase (Stage 1): Ulocuplumab Weekly Dosing (CA212115)**

Procedure	Ulocuplumab administered every week Nivolumab administered every 2 weeks		Notes
	Week 1, 3, 5, 7, 9, etc Ulocuplumab + Nivolumab dosing visits	Week 2, 4, 6, 8, 10, etc Ulocuplumab dosing visits	
Safety Assessments			
Targeted Physical Examination	X	X	Within 72 hours prior to dosing.
Vital Signs and Oxygen Saturation	X	X	Including BP, HR, respiratory rate, temperature and oxygen saturation by pulse oximetry. Pulse oximetry at rest within 72 hours prior to dosing.
Weight	X		Nivolumab dosing calculations should be based on body weight. If the subject's weight on the day of dosing differs by > 10% from the weight used to calculate the dose, the dose must be recalculated. All doses should be rounded to the nearest milligram.
ECOG Status	X		
ECG (12-lead)	See Notes		Every 6 weeks from first dose for the first 12 weeks, then every 12 weeks ( $\pm$ 1 wk)
Adverse Events Assessment	Continuous		
Review of Concomitant Medications	X	X	
Chest X-Ray		X	Week 2 only (monitor for pulmonary toxicity)
Laboratory Tests	X	X	On-study local laboratory assessments should be done within 72 hours prior to each dose: total protein, CBC w/differential, ALT, AST, total bilirubin, direct bilirubin (reflex testing when total bilirubin is elevated), alkaline phosphatase, BUN or serum urea level, uric acid, creatinine, albumin, Ca, Mg, Na, K, P, Cl, LDH, glucose, amylase, lipase, TSH (Free T4 and Free T3 reflex testing if TSH result abnormal).

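### Grade 3 thrombocytopenia of exactly 7 days is assigned to neither duration rule; at DL-1 the literal text could treat a first such event more severely than a somewhat longer one (minor)

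*Protocol*

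**What the plan says.** **Delay rule.** Protocol 4.5.1.2 lists "Grade 3 thrombocytopenia $< 7$ days", without Grade 2 or higher hemorrhage, among the laboratory abnormalities that do not call for a nivolumab delay. Section 4.5.1.1 carries the exemption to ulocuplumab: delay for Grade 3 or higher drug-related events, including "laboratory abnormalities except for Grade 3 AEs that do not require nivolumab dose delay".

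**Resumption rule.** Table 4.5.2.1-1 has two rows that matter here.
- Row 1 (general) takes any Grade 3 or higher drug-related event "except for Grade 3 hematologic AEs listed below or other exceptions listed in section 4.5.1". Its DL-1 cell reads "1st event: Discontinue ulocuplumab".
- Row 2 (hematologic) takes "Any Gr3 drug-related neutropenia, Gr3 thrombocytopenia > 7 days". Its DL-1 cell reads "2nd event: Discontinue ulocuplumab" and gives no first-event instruction.

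**DLT rule.** Under Protocol 3.1.4 and SAP 2.1.1, a hematologic toxicity is a DLT by grade only at Grade 4. A Grade 3 event becomes one through a ulocuplumab dose reduction, a ulocuplumab delay of more than 14 days, or discontinuation. The protocol's discontinuation bullet is "Any toxicity managed by discontinuation of ulocuplumab", with a pointer to 4.5.3.1. The SAP bullet covers both drugs and has no pointer.

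**Laboratory timing.** Table 5.1-2 states "On-study local laboratory assessments should be done within 72 hours prior to each dose", so sampling is roughly weekly under weekly dosing.

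**The concern.** Two limits meant to split one toxicity by duration should meet. Here both are strict, and a duration of exactly 7 days lies between them. The delay itself is clear, since such an event is not exempt. What is unclear is which row governs resumption. If row 1 does, the result at DL-1 is not monotone: 6 days is exempt, 7 days means discontinuation, and 8 days means a hold.

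SAP section 2 says that DL-1 has been opened and allows no ulocuplumab dose reduction. Protocol 3.1.1 makes a cohort intolerable at 2 or more DLTs in up to 6 evaluable subjects, and an intolerable DL-1 stops enrollment for that tumor type. The classification of one event can therefore matter.

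**Working it through.** The documents state no figure on this point, so there is none to reproduce. The check has three parts.

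**1. The rules applied to a first, drug-related, non-bleeding Grade 3 event with a ulocuplumab delay of at most 14 days.** The general row is taken literally, and the discontinuation bullet is read without its pointer.

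| Level | Duration | Rule reached | Action | DLT on this reading |
|---|---|---|---|---|
| DL-1 | 6 days | exempt (4.5.1.2) | no hold | no |
| DL-1 | exactly 7 days | row 1 | discontinue | yes |
| DL-1 | 8 or 14 days | row 2 | hold, not discontinued | no |
| DL1, DL2 | 6 days | exempt (4.5.1.2) | no hold | no |
| DL1, DL2 | exactly 7 days | row 1 | resume at lower dose | yes, by reduction |
| DL1, DL2 | 8 or 14 days | row 2 | resume at lower dose | yes, by reduction |

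The reversal appears only at DL-1. At DL1 and DL2 both rows lead to a reduction at the first event, so the choice of row does not alter DLT status. At DL-1 it also disappears for a second event (row 2 then discontinues) and for a delay of more than 14 days (a DLT by the delay bullet).

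**2. Effect on the cohort decision.** With one other DLT among 6 evaluable subjects:
- event not counted: 1/6, tolerable;
- event counted: 1 + 1 = 2, so 2/6, intolerable.

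**3. What the laboratory schedule can show.** Inputs are a draw 0 to 3 days before each dose (Table 5.1-2) and weekly dosing within 1 day of schedule, at least 6 days apart (Protocol 4.5). Let s1, s2 be the dose shifts in days and a1, a2 the lead times from draw to dose:

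gap between consecutive draws = 7 + (s2 − s1) − (a2 − a1)

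With equal weight on every allowed combination (an assumption), the share of gaps equal to exactly 7 days is:
- doses on schedule, fixed lead time: 100%;
- doses on schedule, lead time free over 0 to 3 days: 4/16 = 25%;
- doses shifted up to 1 day, fixed lead time: 3 of the 8 allowed shift pairs = 37.5%;
- both free: about 20%.

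Seven days is the most frequent gap in each scenario. But a gap between draws is not an event duration. Suppose draws are 7 days apart, the first is Grade 3, and the draws on either side are not. The true duration then lies anywhere between 0 and 14 days. Measured from first abnormal to first recovered draw it is 7 days by subtraction and 8 by inclusive counting. The documents do not say which count applies.

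**The case against.** **Row 1 may not apply.** It excludes the hematologic events listed below it, and Grade 3 thrombocytopenia is one of those by name. On that reading there is no reversal. This is a fair alternative, but the listed item carries its duration limit, and under this reading a 7-day event has a hold with no resumption instruction. The gap changes form and remains.

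**The DLT step is weak.** The protocol bullet points to 4.5.3.1, which names Grade 3 or higher thrombocytopenia with bleeding and recurring events needing multiple reductions. It does not name a first non-bleeding Grade 3 event; only investigator judgment could bring one in. This objection stands against treating the DLT as certain. It also shows that the protocol and SAP bullets differ in reach.

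**The row 2 contrast rests on an irregular cell.** The DL-1 entry starts at the second event, and the DL1 entry passes from the first event to the third. This may be a layout fault. The comparison holds for the text as it reads, and no more.

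**A reader might infer that any longer event escapes DLT status.** The documents do not support that. A delay of more than 14 days, or a second event, can reach a DLT. Without a DLT, a subject who misses two of the six weekly ulocuplumab doses (6 − 2 = 4, below the required 5) is not DLT-evaluable and is replaced.

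**A reader might also infer that 7 days is the usual recorded duration.** The documents show only roughly weekly sampling. Section 5.3 calls for extra tests when clinically indicated, and gaps between draws are not durations.

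**Human review intervenes.** Section 4.5.2.1 is permissive about modification and brings in the Medical Monitor, section 7 provides regular safety calls, and SAP 7.6.1 admits other safety data. This lowers the chance of a wrong decision; it does not tell a site which row to use.

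**Conclusion.** The point holds as a minor internal inconsistency. The delay exemption ends below 7 days and the hematologic row begins above 7 days, so exactly 7 days is delayed without a clear resumption rule. On the literal text it falls to row 1.

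The possible reversal is confined to a first, non-bleeding event at DL-1, compared with a longer first event whose delay is at most 14 days. It assumes that row 1 applies, that the row 2 DL-1 cell is as it reads, and, for DLT status, that the discontinuation bullet is not limited by its pointer to 4.5.3.1. The largest consequence is one DLT, which decides the cohort only when there is exactly one other. No probability can be attached, because the documents give no frequency for this event and no rule for counting its duration.

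**What to change.** Reconcile Table 4.5.2.1-1 with 4.5.1.1 and 4.5.1.2 so that every duration is covered exactly once. The sponsor decides which side 7 days belongs to. In the same amendment:
- state how duration is counted from dated laboratory results;
- check the DL-1 and DL1 cells of the hematologic row for missing entries;
- make the discontinuation bullets in Protocol 3.1.4 and SAP 2.1.1 agree with each other and with the reconciled table, including whether 4.5.3.1 limits them.

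The cost is one inequality sign, a counting sentence and aligned cross-references. No visit, test or subject is added.

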**4.5.2.2 Nivolumab Dose Modification Criteria**

Inpatient dose modifications of nivolumab for the management of toxicities are not permitted. Dose delay criteria for nivolumab can be found in section 4.5.1.2.

**4.5.3 Discontinuation Criteria**

**4.5.3.1 Ulocuplumab Discontinuation Criteria**

Discontinuation criteria apply for all drug-related AE attributed to ulocuplumab and consist of the following:

- Grade ≥ 3 thrombocytopenia associated with bleeding (occurring concomitant with ≥ Grade 2 hemorrhage)

- Grade  $\geq 3$  drug-related infusion reaction of any duration
- Any Grade 4 drug-related AE or laboratory abnormality except for Grade 4 AE listed as exceptions to the nivolumab discontinuation criteria (see section 4.5.3.2)
- Any recurring drug-related Grade  $\geq 3$  AE or laboratory abnormality that requires multiple dose reductions of ulocuplumab (see specific criteria in [section 4.5.2.1](#))
- Any drug-related AE resulting in dose delay of ulocuplumab  $> 6$  weeks
- Any AE, laboratory abnormality, or intercurrent illness which, in the judgment of the Investigator, presents a substantial clinical risk to the subject with continued ulocuplumab dosing

#### **4.5.3.2 Nivolumab Discontinuation Criteria**

Discontinuation criteria apply for all drug-related AE attributed to nivolumab and consist of the following:

- Any Grade 2 drug-related uveitis, eye pain, or blurred vision that does not respond to topical therapy and does not improve to Grade 1 severity within the re-treatment period OR requires systemic treatment
- Any Grade 3 non-skin, drug-related adverse event lasting  $> 7$  days, with the following exceptions for drug-related laboratory abnormalities, uveitis, pneumonitis, bronchospasm, diarrhea, colitis, neurological toxicity, hypersensitivity reactions, and infusion reactions:
  - Grade 3 drug-related uveitis, pneumonitis, bronchospasm, diarrhea, colitis, neurologic toxicity, hypersensitivity reaction, or infusion reaction of any duration requires discontinuation
  - Grade 3 drug-related endocrinopathies adequately controlled with only physiologic hormone replacement do not require discontinuation
  - Grade 3 drug-related laboratory abnormalities do not require treatment discontinuation except:
    - ◆ Grade 3 drug-related thrombocytopenia associated with bleeding requires discontinuation
    - ◆ Any drug-related liver function test (LFT) abnormality that meets the following criteria require discontinuation:
      - If a subject has a baseline AST or ALT within normal limits:
        - AST or ALT  $> 5-8x$  ULN for  $> 2$  weeks
        - AST or ALT  $> 8x$  ULN, irrespective of duration
        - Concurrent AST or ALT  $> 3x$  ULN and total bilirubin  $> 2x$  ULN
      - If a subject has a baseline AST or ALT within Grade 1 or 2 toxicity range:
        - AST or ALT  $> 10x$  ULN for  $> 2$  weeks
        - AST or ALT  $> 15x$  ULN, irrespective of duration
        - Total bilirubin  $> 5x$  ULN
        - Concurrent AST or ALT  $> 3x$  ULN and total bilirubin  $> 2x$  ULN

- Any Grade 4 non-skin drug-related adverse event or laboratory abnormality, except for the following events which do not require discontinuation:
  - Isolated Grade 4 electrolyte imbalances/abnormalities that are not associated with clinical sequelae and are corrected with supplementation/appropriate management within 72 hours of their onset
  - Grade 4 thrombocytopenia or neutropenia < 5 days
  - Grade 4 lymphocytopenia or leukopenia not associated with symptoms or clinical manifestations. It is recommended to consult with the BMS Medical Monitor for Grade 4 lymphocytopenia.
  - Grade 4 amylase or lipase abnormalities that are not associated with symptoms or clinical/radiographic manifestations of pancreatitis. It is recommended to consult with the BMS Medical Monitor for Grade 4 amylase or lipase abnormalities.
  - Grade 4 drug-related endocrinopathy adverse events, such as adrenal insufficiency, ACTH deficiency, hyper- or hypothyroidism, or glucose intolerance, which resolve or are adequately controlled with physiologic hormone replacement (corticosteroids, thyroid hormones) or glucose-controlling agents, respectively, may not require discontinuation after discussion with and approval from the Medical Monitor.
- Any dosing delay lasting > 6 weeks with the following exceptions:
  - Dosing delays to allow for prolonged steroid tapers to manage drug-related AEs are allowed. Prior to re-initiating treatment in a subject with a dosing delay lasting > 6 weeks, the BMS Medical Monitor must be consulted. Tumor assessments should continue as per protocol even if dosing is delayed.
  - Dosing delays > 6 weeks that occur for non-drug-related reasons may be allowed if approved by the BMS Medical Monitor. Prior to re-initiating treatment in a subject with a dosing delay lasting > 6 weeks, the BMS Medical Monitor must be consulted. Tumor assessments should continue as per protocol even if dosing is delayed.
- Any adverse event, laboratory abnormality, or intercurrent illness which, in the judgment of the Investigator, presents a substantial clinical risk to the subject with continued ulocuplumab or nivolumab dosing

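### Protocol 4.5.3.2 exempts Grade 4 thrombocytopenia of under 5 days from the nivolumab stop without a bleeding limit, so with Grade 2 or short Grade 3 hemorrhage it has a weaker mandatory rule than Grade 3 thrombocytopenia with the same bleeding

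*Protocol*

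**What the plan says.** Protocol 4.5.3.2 governs when nivolumab must be stopped for events attributed to it. Grade 3 laboratory abnormalities generally do not require a stop, but one exception reads "Grade 3 drug-related thrombocytopenia associated with bleeding requires discontinuation". It has no duration limit.

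Grade 4 non-skin events and laboratory abnormalities require a stop, "except for the following events which do not require discontinuation". Five items follow:

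- "Isolated Grade 4 electrolyte imbalances/abnormalities that are not associated with clinical sequelae", with a time limit for correction
- "Grade 4 thrombocytopenia or neutropenia < 5 days"
- "Grade 4 lymphocytopenia or leukopenia not associated with symptoms or clinical manifestations"
- "Grade 4 amylase or lipase abnormalities that are not associated with symptoms" or signs of pancreatitis
- endocrinopathies that resolve or are controlled, which "may not require discontinuation after discussion with and approval from the Medical Monitor"

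For ulocuplumab, Protocol 4.5.3.1 writes the bleeding stop as "Grade ≥ 3 thrombocytopenia associated with bleeding (occurring concomitant with ≥ Grade 2 hemorrhage"). It also exempts from its general Grade 4 stop whatever is on the nivolumab exception list.

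Protocol 3.5 makes the criteria in both sections compulsory reasons to discontinue.

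**The concern.** A bleeding stop should not become weaker as the platelet count falls. Here it does for short events. At Grade 3 with bleeding, nivolumab is permanently discontinued. At Grade 4 for fewer than 5 days, the text says discontinuation is not required, whether or not the subject bled.

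What is at stake is re-exposure after a bleeding event. Nivolumab is held for the Grade 4 event under 4.5.1.2, but 4.5.1.3 allows it to resume once the event is back to Grade 1 or baseline. If the event is attributed to both drugs, ulocuplumab is stopped under 4.5.3.1 while nivolumab need not be, and SAP 7.4.2.3 provides for subjects who continue on nivolumab alone. Bleeding with low platelets is foreseeable, since Protocol 3.4.1 permits low-dose aspirin, warfarin and heparin.

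**Working it through.** No sample size, error rate or event count is involved, so the check sets the rules side by side.

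**Step 1: which bleeding counts.** The Grade 3 bullet in 4.5.3.2 gives no hemorrhage grade. Two neighbouring rules do. Protocol 4.5.1.2 waives a nivolumab delay for Grade 3 thrombocytopenia under 7 days unless there is hemorrhage of Grade 2 or higher, and 4.5.3.1 explains its bleeding stop in the same terms. I therefore read bleeding in 4.5.3.2 as Grade 2 or higher.

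**Step 2: what the hemorrhage triggers by itself.** Under 4.5.3.2, drug-related hemorrhage stops nivolumab in its own right if it is Grade 4, or if it is Grade 3 for more than 7 days. Taking the hemorrhage as drug-related, what remains is Grade 2 hemorrhage, and Grade 3 hemorrhage of 7 days or less.

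**Step 3: the mandatory rule for that remaining bleeding.** Each column assumes the thrombocytopenia is attributed to that drug.

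| Thrombocytopenia | Nivolumab (4.5.3.2) | Ulocuplumab (4.5.3.1) |
|---|---|---|
| Grade 3, any duration | Stop | Stop |
| Grade 4, under 5 days | Not required | Stop |
| Grade 4, 5 days or more | Stop | Stop |

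The nivolumab column is out of order in the middle row only. At 5 days or more, Grade 4 requires a stop with or without bleeding, so there the rule is stricter than at Grade 3.

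**Step 4: comparison with the other Grade 4 exceptions.** Four of the five carry a clinical condition: no sequelae, no symptoms (twice), or resolution or control with Medical Monitor approval. The platelet and neutrophil item is the only one limited by duration alone.

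**Step 5: size of the window.** Counted in whole days, under 5 days means 1 to 4 days, which fits inside one 14-day nivolumab interval.

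**Step 6: effect elsewhere.** Protocol 3.1.4 counts drug-related Grade 4 thrombocytopenia as a DLT. Its only exceptions are amylase or lipase, and lymphocytopenia, without symptoms. DLT counts therefore do not depend on this exception.

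**The case against.** The strongest reply is that other provisions already deal with the case.

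- Protocol 3.5 requires a stop whenever the investigator judges that continuing is not in the subject's best interest, and 4.5.3.2 ends with a similar judgment criterion.
- Both drugs are held in the meantime, because 4.5.1.2 delays ulocuplumab when nivolumab is delayed for an AE.
- Grade 4 platelets usually recover through Grade 3. If bleeding persists then, the Grade 3 bullet can be applied.
- With weekly dosing, laboratory tests are scheduled before each weekly dose (Protocol Table 5.1-2), so showing that an event lasted under 5 days would generally need extra platelet counts.

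All of this stands as mitigation and makes actual re-exposure less likely. None of it makes a stop mandatory while platelets are at Grade 4. The judgment criteria apply equally at Grade 3, where the plan still wrote a fixed stop. Use of the Grade 3 bullet during recovery is an interpretation that sites may not share.

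A second reply is that the wording may be deliberate. The Protocol's document history says Amendment 04 aligned these criteria with nivolumab program language, and the shared item with neutropenia could be a duration rule for brief falls in counts. That is possible. The comparison in step 4 suggests an omission but does not prove one. The inversion is in the text either way.

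A reader might also infer that Grade 1 bleeding belongs to the gap, since the Grade 3 bullet names no hemorrhage grade. The documents do not support this well. Under 4.5.1.2, Grade 3 thrombocytopenia under 7 days with only Grade 1 bleeding needs no delay, and it would be odd for the same event to require permanent discontinuation.

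**Conclusion.** The point holds in a narrow form. Grade 4 thrombocytopenia of under 5 days attributed to nivolumab, with Grade 2 hemorrhage or with Grade 3 hemorrhage of 7 days or less, has a weaker mandatory rule than the same bleeding at Grade 3 platelets. Ulocuplumab's own bleeding rule does not have this gap.

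The conclusion rests on reading bleeding as Grade 2 or higher, in line with 4.5.1.2 and 4.5.3.1, and on the exception list meaning what it says. The documents give no frequency for the event, and it may be rare.

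Two wider inferences should be resisted. Grade 4 thrombocytopenia as a whole is not under a laxer rule than Grade 3; only the short, bleeding case is. Nor do the documents show that subjects would in practice be restarted after such a bleed; they show only that a stop is not required. DLT counts, sample size, power and alpha are unaffected. This is a minor correction to a safety rule.

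**What to change.** In the Grade 4 exceptions of Protocol 4.5.3.2, replace the combined item with two:

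- *Grade 4 thrombocytopenia < 5 days not associated with Grade ≥ 2 hemorrhage*
- *Grade 4 neutropenia < 5 days*

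The hemorrhage grade should be stated. Without it, the new wording could be read as requiring a permanent nivolumab stop for Grade 1 bleeding, which is out of line with 4.5.1.2 and 4.5.3.1.

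Because 4.5.3.1 imports this exception list, the effect on ulocuplumab needs checking. With the Grade 2 qualifier no new ulocuplumab stop arises, since its own bleeding bullet already covers Grade 4 platelets with hemorrhage of Grade 2 or higher. Sections 4.5.1.2 and 3.1.4 need no change.

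The cost is one phrase, with no added subjects, visits or tests. A few more subjects may have to stop nivolumab, limited to those with this event, and no existing stop is loosened.
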